5. DATA COLLECTION

Data Collection Procedures

The study will include 4 visits to CMH and assessments to be conducted at home.

Participants will receive a Fitbit Alta HR™, a wristworn tri-axial activity monitor with optical heart rate monitoring (**Figure 1**, top), and a Fitbit Aria™ smart scale which measures fat mass and fat-free mass using bioimpedance (**Figure 1**, bottom). Participants will be instructed to wear the monitor at all times (except for swimming or showering) and measure their body composition on the scale daily for 6 weeks. Fitbit_EE and Fitbit_ES will be uploaded using Bluetooth and Wi-Fi, respectively, to the Fitbit Dashboard™ and accessed by study staff using Fitabase™, a research platform that collects data in collaboration with Fitbit, Inc. Fitbit_EE and Fitbit_ES will be calibrated during two 14-day assessment periods (study start and study end) using DLW and DXA. ‘True’ EE will be measured using a standard 14-day DLW protocol¹⁹ with samples collected on Day 0, 7, and 14. ‘True’ ES will be calculated using DXA measurements on Day 0 and Day 14. Fitbit_EE and Fitbit_ES during the assessment period will then be calibrated to ‘true’ EE and ES using a Bayesian semi-parametric approach, using free knot splines and Reversible Jump MCMC algorithms previously developed through work in our lab.¹⁸ This calibration model will then be applied to daily Fitbit_EE and Fitbit_ES collected during the middle 14-day assessment period to assess daily energy balance. Finally, we will estimate EI from Fitbit measurements using the equation^{16, 17}:

$$\text{calculated energy intake} = 1,020 \frac{\Delta FFM}{\Delta t} + 9,500 \frac{\Delta FM}{\Delta t} + EE$$

Where ΔFFM and ΔFM represent change in each variable; Δt represents days between start and end of an assessment period; 1,020 represents the energy density in kcals of FFM per kg; and 9,500 represents the energy density of FM per kg, both based on established values;²⁰ EE represents daily energy expenditure during the assessment period.

Doubly-labeled Water Procedures

- Energy expenditure will be assessed using the doubly labelled water (DLW) technique over a two week period. The DLW technique uses enhanced levels of naturally occurring stable (i.e., non-radioactive) isotopes of hydrogen (deuterium; ^2H) and oxygen (^{18}O) to accurately measure energy expenditure via indirect calorimetry in free-living organisms. DLW was first introduced for human use in 1982. The method is safe and has been validated extensively in both humans and other animals (including children and infants). Participants will be administered a dose of DLW with 1.5 ml/kg body weight of a mixture of 10% enriched H_2^{18}O , and 99% enriched $^2\text{H}_2\text{O}$ (Cambridge Isotopes, Cambridge, MA). Participants will provide a urine sample (>15 mL) on day 0, 7, and 14, which will be analyzed by Pennington Biomedical Research Center to calculate elimination rates of the isotopes from the body.

Figure 1. Fitbit Alta HR (top) and Aria (bottom).

DXA Procedures

- Assessment of body composition, including fat mass, fat free mass, and visceral adipose tissue, will be completed using dual energy X-ray absorptiometry (DXA). DXA is a non-invasive procedure which participants will lie on a table and a detector will be passed over the body. The procedures involves approximately 1/3 the radiation in a normal chest X-ray and should take approximately 10 – 20 minutes. All anthropometric measurements will be performed with the participant dressed in surgical scrubs and in bare feet. BMI (weight [kg]/height [m]²) will be calculated from the average of three height and weight measurements using a wall-mounted stadiometer and electronic scale and recorded to the nearest 0.1 cm and 0.1 kg, respectively.

Diet Recalls

- Energy intake will be assessed subjectively via interviewer-administered dietary recalls. Three dietary recalls will occur on randomly selected non-consecutive days over each one-week treatment condition (including at least one weekend day) to minimize preparation that could bias recall by the participants. All interviews will be conducted over the telephone, will ask about all foods consumed over the previous 24 hours using a multi-pass approach, and energy intake will be calculated using the Nutrient Data System for Research software (NDSR Version 2014).

Records to be kept

Data collected will be deidentified with a subject ID number. A linking list will be used, which will contain the subject ID, subject's name, gender, and date of birth. This log will only be accessible by the PI and the study team.

Secure Storage of Data

Consent statements and participant data will be kept in separate locked file cabinets so that individuals are not easily connected to the study results. All digital data will be stored on a firewall and password-protected project server at Children's Mercy Hospital. Data collected at the CMH Don Chisholm Center CMH will be analyzed and stored in secure shared drive at the Don Chisholm Center.

Fitabase Data Security:

Data from the Fitbits will be monitored and reported to our research team in real-time using the Fitabase software (Small Steps Labs, LLC, San Diego, CA). Fitabase is an independent software company that provides real-time data from the Fitbit to researchers via an application program interface. Thus, we may be provided with real-time information regarding wear time and also minute-by-minute information regarding activity intensity (e.g. sedentary, moderate, etc.). Only participant ID# will be associated with this data. We will create fitbit accounts for everyone using a generic email account with many associated logins. We will not use participant names or actual birthdates (only birthyear) so no identifying information is associated with the account.

6. STUDY DURATION/STUDY TIMELINE

Target start date is July 2017

Stage 2, recruitment and data collection, January 2018 – June 2018

Stage 3, data analysis and manuscript development, June 2018- August 2018

Total study duration will be 1 year.

We will recruit potential participants from the community, which could include CMH patients, employees, or students. We plan to post a recruitment flyer within CMH in clinic areas and employee breakrooms, as patients, employees, or students would be eligible to participate. Potential participants from the community will then contact us from the information on the flyer if they are interested in the study.

Once potential participants are identified and express interest, we will schedule an orientation (visit 1) at CMH Don Chisholm during which informed consent will be obtained. Participants will be given the Actigraph activity monitor, the FitBit tracker, the FitBit scale, and be trained on how to use them. Participants will complete the DXA and the DLW procedures. The day zero urine sample will be obtained at visit 1.

After visit 1, participants will be asked to complete the urine samples at home (day 8). Participants will also be contacted to complete the diet recall procedures. Participants will be asked to wear the FitBit tracker and use the FitBit Scale daily starting at visit 1 until the end of the study. The Actigraph monitor will be worn between visit 1 and 2, and visit 3 and 4.

Visit 2 will occur 2 weeks after visit 1. Urine samples will be returned. A DXA will be obtained.

Visit 3 will occur 4 weeks after visit 1. Procedures at visit 3 are identical to visit 1.

Visit 4 will occur 2 weeks after visit 3. Procedures at visit 4 are identical to visit 2.

7. STATISTICAL CONSIDERATIONS

Measures

- Primary measures: Energy intake, energy expenditure and body composition
- Secondary measure(s): Demographics

General Design Issues

The proposed pilot study is a calibration study, which will generate data needed for a larger study.

Sample size determination

As a pilot study, we will have resources to collect data from N=24 participants. We will use this data to determine power requirements for a larger study.

Data Analyses

Statistical significance for comparison between the different data collection methodologies will be tested using analysis of variance (ANOVA) for continuous variables and chi-square tests for categorical variables. Statistical significance will be set at P<.05 (two-sided) for all analyses.

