1. STUDY OBJECTIVES/HYPOTHESIS

Our research group has successfully developed a system of assessment methodologies and statistical techniques that can accurately assess energy balance and estimate energy intake [EI] using research-grade but non-gold standard techniques.¹⁶⁻¹⁸ The purpose of this study is to apply these techniques using consumer devices to assess rate of energy storage [ES] and energy expenditure [EE], then estimate EI using the intake-balance technique.

We believe calibration models developed in the proposed study will be able to be translated to other consumer devices with only minor modifications given common hardware (e.g. triaxial accelerometry), resulting in overall improved ability to assess energy balance and EI at a population level and positive health outcomes.

Aim 1. Validate and calibrate consumer devices to estimate energy balance using gold-standard methods and a Bayesian semi-parametric approach. *Hypothesis 1:* We will be able to jointly model measurement error for both EE and ES to create a calibration model that reduces bias and improves accuracy of consumer devices of EE and ES.

Aim 2. Estimate energy intake using the intake-balance technique using consumer monitors. *Hypothesis 2:* We will use calibrated EE and ES from consumer monitors to estimate EI using the intake-balance technique, with values being superior to self-reported EI.

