8. HUMAN SUBJECTS

Institutional Review Board (IRB) Review and Informed Consent

The IRB of record is Children's Mercy Hospital.

This protocol, and any subsequent modifications, will be reviewed and approved by the Pediatric IRB at The Children's Mercy Hospital & Clinics.

Potential participants will be recruited from the community.. Once the participants are contacted by CMH study staff, they will be given more details about the study and sent the consent form to review.

The study team will do a 10 minute phone screening with the parent to determine eligibility, and will schedule a time for the parent and child to come in for an orientation. The parent and child will then come to the Don Chisholm center at CMH for visit 1. The consent form will be reviewed and ample time will be given for the parent and child to consider participation. Prior to performing any procedures related to this study, the permission/assent form or consent form will be reviewed carefully with the participant and parent in person.

Subject Confidentiality

All records will be kept in a locked file cabinet. Human subject's names will be kept on a password protected database and will be linked only with a study identification number for this research. There are no patient identifiers recorded in the research record. All computer entry and networking programs will be done using study identification only. All data will be entered into a computer that is password protected. Data will be stored in a locked office of the investigators and maintained for a minimum of three years after the completion of the study.

Subject Payment

Subjects will be paid via ClinCard \$50 total for participation. Payment will be given in \$25 increments at visit 2 and visit 4 once the Actigraph activity monitor is returned. SSN is required for payment, and will be entered directly into the Greenphire secure website. SSN will not be retained in the subject's study file. Participants may also be compensated for mileage or a hotel stay based on their distance traveled (they will be given a choice of one or the other).

Participants will be able to keep the Fitbit Alta HR™ activity tracker (\$150 value) and the Fitbit Aria™ smart scale (\$130 value). If participants are within the same family, they will be given one Fitbit Aria™ smart scale per household.

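### The ANOVA named for comparing methods tests average values, so it cannot show that calibration improves accuracy or that Fitbit-based energy intake is superior to self-report

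*Protocol*

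**What the plan says.** Section 1 sets two hypotheses. Under Aim 1 the investigators expect to "create a calibration model that reduces bias and improves accuracy of consumer devices of EE and ES", where ES is the rate of energy storage. Under Aim 2 they will estimate EI from calibrated Fitbit data, "with values being superior to self-reported EI". No reference or measure for that superiority is given.

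Section 7 lists "Primary measures: Energy intake, energy expenditure and body composition" and then gives the analysis: "Statistical significance for comparison between the different data collection methodologies will be tested using analysis of variance (ANOVA) for continuous variables", at two-sided P<.05 for every analysis. The sample is 24 people, set by resources. On its use, the section says: "We will use this data to determine power requirements for a larger study".

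Three other places bear on the point:
- **Criterion data.** Section 5 says "Fitbit_EE and Fitbit_ES will be calibrated during two 14-day assessment periods (study start and study end) using DLW and DXA" and applies the resulting model to the middle period. Section 3, stage 4, instead describes the third period as one in which the validation and calibration models are reassessed against DLW and DXA.
- **Diet recalls.** Section 5 says "Three dietary recalls will occur on randomly selected non-consecutive days over each one-week treatment condition". The design in Section 3 has 14-day assessment periods and no treatment conditions.
- **Families.** Sections 4 and 8 allow relatives to enrol, and Section 8 adds: "If participants are within the same family, they will be given one Fitbit Aria™ smart scale per household".

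**The concern.** Accuracy and superiority, as Section 1 uses them, are about how close each person's value lies to that person's criterion value. ANOVA on the listed measures asks whether methods differ on average. A method can match the criterion mean exactly and still be far out for most individuals. Another can be a little low for everyone and close for each.

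A non-significant ANOVA could therefore be read as validity, and a significant recall-versus-criterion difference could be read as Fitbit superiority, when neither follows. No other section supplies an error comparison. Section 3 promises validation without naming a measure of agreement. The Bayesian model in Section 5 estimates the calibration but is given no test of whether it lowers error.

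A separate statistical analysis plan could add agreement statistics, and their absence from the protocol is not the point. The point is that Section 7 does name a test, and that test does not match the hypotheses.

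**Working it through.** The protocol gives no bias, SD, effect size or power, so there is no planned figure to reproduce. From the documents: n = 24, two-sided 5% level, and the intake equation in Section 5. **Every bias and SD below is assumed** (kcal/d, written bias/SD, normal errors). Section 7 names no follow-up tests. As an illustration, each method's mean is compared with the criterion by a within-person t-test, either directly (pairwise) or only after a significant repeated-measures F (gated).

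**Formulas.** RMSE = √(bias² + SD²). The means test has non-centrality |bias|/(SD/√24), with critical value 2.069 on 23 df. The alternative is a paired t-test on |Fitbit − criterion| − |recall − criterion|.

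**1. Both unbiased, RMSE 300 v 600.** The means test flags each method in 5%. The repeated-measures F rejects in 5% and a one-way F in 0.4%. For absolute error:
- mean difference = (600 − 300) × √(2/π) = 239
- SD = √(300² + 600²) × √(1 − 2/π) = 404
- ratio = 239/404 = 0.59, giving about 79% power by the t approximation and 82% by simulation.

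A separate run with SDs of 200 to 800 against 100 gave 4.7–5.3% rejection for the two-method repeated-measures ANOVA. The size of the accuracy gap does not register.

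**2. Equal closeness, RMSE 500 each (Fitbit 0/500, recall −300/400).** Recall non-centrality is 300/(400/√24) = 3.67, power 94%. Only recall is flagged in 0.94 × 0.95 = 89% pairwise, and in 70% gated. The absolute-error test favours Fitbit in 3% and recall in 2%.

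**3. Less biased or equally biased method noisier.**

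| Setting | Wrong method favoured, pairwise | Gated | Absolute-error test finds the closer method |
|---|---|---|---|
| Fitbit SD 700, bias 0/100/200/300; recall −300/200 | 95/90/73/48% | 54/65/62/44% | 74–85% |
| Recall SD 600, bias 0/−100/−200/−300; Fitbit 150/200 | 89/82/61/33% | 13/26/31/22% | 95–98% |

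In the last two columns of recall bias (−200 and −300), recall is the more biased as well as the noisier method; the wrong-way share falls but does not vanish, because its noise hides its bias.

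**4. Recall biased and noisier, Fitbit unbiased (Fitbit 0/250, recall SD 500).** At recall bias −400/−300/−200 the means test points the right way in 92/76/44% pairwise and 90/72/39% gated. The absolute-error test does so in 98/95/89%.

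**5. Imperfect criterion.** By the Section 5 equation, 1 kg of fat mass over 14 days is 9,500/14 = 679 kcal/d. An EI criterion error of SD 300 thus equals 300 × 14/9,500 = 0.44 kg error in fat-mass change. Criterion error of SD 150/300/450 lowers the 82% in step 1 to about 73/52/35%. Type I error stays near 5%.

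**6. Households.** In four assumed layouts of 24 people (five pairs plus 14 singles, 12 pairs, 8 triples, 6 fours; intraclass correlation 0.1–0.5), a t-test on household means has about 45–78% power for RMSE 300 v 600, against 78–83% when households are ignored. With criterion SD 300 the figures are about 28–48% against 51–53%. Ignoring households raises type I error to at most 12%, with six families of four at correlation 0.5.

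**The case against.** **Hypothesis 1 is not left to ANOVA alone.** Aim 1 names a Bayesian measurement-error model, which handles device error against DLW and DXA directly, and ANOVA does address average bias. Both are true. The model still estimates a calibration without a stated comparison of error before and after it, so the accuracy half stays open. The mismatch is plainest for Hypothesis 2.

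**Section 7 does not say that ANOVA is run on raw values.** It could be run on error scores. But the measures listed are values and no error score is defined, so the plain reading is values.

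**The sizes are illustrative.** This stands. They rest on assumed errors and on follow-up tests the protocol does not name, and the pairwise and gated results differ widely in step 3. What does not depend on them is that a test of means is blind to spread around the criterion.

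**Two stronger readings are tempting and not supported.**
- A reader might infer that no criterion data exist outside the calibration fit unless people are left out. Section 3, stage 4, can be read as fitting on the first period and checking on the third, which would give such data. Section 5 calibrates on both periods. The two sections conflict and need reconciling; they do not show that out-of-fit data are absent.
- A reader might infer that the pilot cannot inform the larger study. Section 7 says that the data will be used, not the ANOVA output. The SD of the error difference can be computed wherever recalls fall in a criterion period, whatever test is named.

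**Conclusion.** The concern holds in limited form. The named ANOVA can speak to average bias. It cannot show that calibration improves accuracy, nor that Fitbit EI is superior to self-report. If both methods are unbiased it rejects at about 5% however far apart their errors are, and if the less biased method is the noisier one it can point the wrong way. It does not always mislead: where recall is both biased and noisier than an unbiased Fitbit, it usually points the right way when the recall bias is large, and mostly loses power when it is small.

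Confidence is high on the mismatch and moderate on the sizes. The consequence is bounded because this is a 24-person pilot whose data can be reanalysed. It should be fixed, since the change is small and relies mainly on measurements already planned.

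**What to change.** **In Section 7**, for the two hypotheses, replace ANOVA of values with within-person comparisons against DLW/DXA in the first and last 14-day periods:
1. Report mean bias with 95% CI and limits of agreement for EE, ES and EI.
2. For Hypothesis 1, compare the absolute (or squared) error of calibrated and uncalibrated Fitbit EE and ES.
3. For Hypothesis 2, estimate |EI_Fitbit − EI_DLW/DXA| − |EI_recall − EI_DLW/DXA| with 95% CI, and report its SD for planning. Use recalls from the same 14-day period, and allow for household where relatives are enrolled, since a shared scale can give them a common ES error.
4. State that a non-significant mean difference will not be read as validity.

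**In Sections 3 and 5**, reconcile the role of the third period, and compute calibrated error only on data not used in the fit. Either fit on the first period and test on the third, or leave out people or households.

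**In Section 5, Diet Recalls**, replace the reference to a one-week treatment condition with the assessment periods that the recalls cover. Section 6 places recall contact after visit 1 but does not settle this for the last period.

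**Cost.** One rewritten paragraph and a few clarifying lines. Leaving people out means up to 24 refits of the calibration model, or 6 if everyone belongs to a family of four. Recalls may have to be added if they were not planned in both criterion periods. At n = 24 the test may be inconclusive, especially with criterion error and household clustering, so the interval should be the main result.

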3. STUDY DESIGN

There are four stages in the proposed project:

1. We will validate EE and ES (hereafter, Fitbit_EE and Fitbit_ES) from a consumer physical activity monitor (Fitbit Alta HR™) and body composition analyzer (Fitbit Aria™) with gold-standard measures of DLW for EE and DXA for ES during an initial 14- day baseline period;
2. We will estimate EI using the intake-balance method during the 14-day baseline period;
3. We will calibrate daily Fitbit_EE and Fitbit_ES from consumer devices using a Bayesian semi-parametric measurement error modeling approach to estimate energy balance during a second 14-day period immediately following the baseline period.
4. We will reassess our validation and calibration models of consumer devices during a third 14-day assessment period to evaluate changes associated with growth and development with gold-standard measures of DLW for EE and DXA for ES.

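### The difference test in Section 7 cannot by itself support the aim of validating the Fitbit devices against DLW and DXA

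*Protocol*

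**What the plan says.** Aim 1 in protocol Section 1 begins "Validate and calibrate consumer devices to estimate energy balance using gold-standard methods". Stage 1 in Section 3 makes this concrete: "We will validate EE and ES (hereafter, Fitbit_EE and Fitbit_ES) from a consumer physical activity monitor" and a body composition scale, "with gold-standard measures of DLW for EE and DXA for ES during an initial 14- day baseline period". Stage 4 reassesses the validation and calibration models in the third 14-day period, again against DLW and DXA.

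Under Data Analyses, Section 7 gives the rule for comparing methods: "Statistical significance for comparison between the different data collection methodologies will be tested using analysis of variance (ANOVA) for continuous variables", with chi-square tests for categorical variables. It adds: "Statistical significance will be set at P<.05 (two-sided) for all analyses". EE and ES are continuous, so the ANOVA is the test that applies to them.

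The sample size is set by resources ("As a pilot study, we will have resources to collect data from N=24 participants"), and power is left for later ("We will use this data to determine power requirements for a larger study").

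Sections 1, 3 and 5 also describe a Bayesian semi-parametric calibration of the device values to the reference values. No criterion is attached to it for calling a device, or a calibrated value, valid.

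**The concern.** To validate a device against a reference method is to show that the two agree closely enough. A two-sided difference test asks something else: whether the data are incompatible with a mean difference of exactly zero. Failure to reject may mean that the bias is small. It may equally mean that the differences are too variable, or the sample too small, for a material bias to be seen. The test does not separate these cases, and for a given bias a noisier device is more likely to give P>.05. Conversely, a precise device with a trivial bias can give P<.05. Pairing the ANOVA correctly does not remove the problem, because the mismatch lies between the form of the test and the question.

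At stake is what the pilot may say about the raw devices after stages 1 and 4. Under Section 7 as written, the report would contain P values for the device-versus-reference comparisons, and neither a large nor a small P value tells a reader whether the mean bias is acceptably small.

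**Working it through.** **Inputs from the protocol (Section 7).** N = 24; two-sided alpha = 0.05; ANOVA for a difference. There is no power figure to reproduce, because N was set by resources.

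**Assumptions.** The protocol gives no SD of device-minus-reference differences, expected bias or margin. I assume a within-person (paired) analysis of all 24 participants, treat them as independent, and express bias as d = mean difference / SD of within-person differences. With two methods, the repeated-measures ANOVA is the paired t test.

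**1. How often a real bias is non-significant.** The test statistic is noncentral t with 23 degrees of freedom and noncentrality d × √24 = d × 4.899. The critical value is t(0.975, 23) = 2.069. P(non-significant) is the probability that the statistic falls between −2.069 and 2.069.

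| Bias d | Noncentrality | P(non-significant) |
|---|---|---|
| 0.2 | 0.98 | 84% |
| 0.3 | 1.47 | 71% |
| 0.5 | 2.45 | 35% |
| 0.6 | 2.94 | 20% |
| 0.8 | 3.92 | 4% |

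With fewer completers, the 0.5 SD row rises to 44% (n = 20) or 48% (n = 18).

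**2. The effect of noise.** Hold an EE bias at an assumed 150 kcal/day and vary the assumed SD of differences. SDs of 200, 300, 400 and 500 kcal/day give d = 150/200 = 0.75, 150/300 = 0.5, 150/400 = 0.375 and 150/500 = 0.3. P(non-significant) is 6%, 35%, 58% and 71%. The bias is the same throughout; only the device's scatter has grown.

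**3. What N = 24 can say about mean bias.** The 95% CI half-width is 2.069/4.899 = 0.42 SD and the 90% half-width is 1.714/4.899 = 0.35 SD. The approximate 95% CI half-width for each limit of agreement is 2.069 × √(3/24) = 0.73 SD.

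**4. How a margin rule would behave.** Suppose agreement is claimed only if the 90% CI lies inside ± a margin (two one-sided tests at 5% each; simulation, 400,000 runs). With an illustrative margin of 0.5 SD, a device biased by exactly the margin is accepted in about 5% of studies. The table in step 1 shows the same bias being non-significant in 35%. With zero true bias at N = 24, agreement is concluded in 22%, 54%, 77%, 85% and 97% of studies for margins of 0.4, 0.5, 0.6, 0.65 and 0.8 SD. The rule is therefore usable at N = 24 when the margin is wide relative to the scatter, and otherwise often returns an inconclusive result.

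**5. Why ES is the harder case.** The intake-balance equation in Section 5 weights fat-mass change by 9,500 kcal per kg, divided by the days in the period. If the within-person difference in fat-mass change had an SD of 0.5 kg (an assumption), the fat term alone would have an SD of 9,500 × 0.5/14 = 339 kcal/day. The 95% CI half-width for mean bias would then be 0.42 × 339, about 143 kcal/day. Both figures scale in proportion to the assumed SD.

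**The case against.** Several points on the other side are sound and limit the finding.

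- **No pass rule is written down.** A reader might infer that non-significance will be reported as validated. The protocol does not say so and states no pass/fail verdict on the device. What stands is narrower: the stated test cannot supply the evidence that the word validate calls for.
- **The null is not plainly what the team hopes to show.** A reader might infer a reversed burden of proof. Hypothesis 1, however, is that calibration reduces bias, which presupposes biased raw devices, and Section 2 says that such devices vary in validity and reliability. A significant raw difference fits that hypothesis.
- **Nothing shows that a wrong verdict would carry into Aim 2.** Because EE enters the intake equation one-for-one, a reader might infer that a missed bias passes into estimated intake. But Hypothesis 2 uses calibrated EE and ES, and neither the calibration nor the intake estimate depends on the ANOVA result. A bias that the ANOVA missed would still be in the data used for calibration. Stage 2 does not say whether its baseline intake estimate uses calibrated values; that is too little to support the stronger reading.
- **The Bayesian calibration is a major planned analysis of device error.** This is true, but validation is named as a task of its own, and the calibration has no agreement criterion either.
- **Margins and intervals may be left to a statistical analysis plan, which is not shown.** This is fair as to their absence. The finding rests on what Section 7 does fix, namely a difference test and a threshold for all analyses.
- **This is a resource-limited pilot.** Low power is not the fault. It only makes non-significance less informative.

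**Conclusion.** The point holds in this limited form: Section 7 fixes a difference test for comparisons whose stated purpose is validation, and that test cannot by itself support validity. The conclusion concerns the form of the test and does not depend on any assumed SD.

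The size does depend on assumptions. The miss rates of 71%, 35% and 4% for biases of 0.3, 0.5 and 0.8 SD apply only to a paired analysis of 24 complete, independent participants, with SD meaning the SD of within-person differences. No single figure should be quoted without those conditions. If the ANOVA treated the methods as separate groups, bias would be scaled by a between-person SD and the figures would not be comparable, so I draw no paired-versus-unpaired contrast. Families may enrol together, which could lower the effective sample size; the protocol gives nothing to quantify this.

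The change should be made, because it is cheap and determines what the pilot can legitimately claim. The finding does not extend to the calibration model or to the Aim 2 comparison with self-reported intake.

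**What to change.** In Section 7, for the stage 1 and stage 4 comparisons of Fitbit_EE with DLW and of Fitbit_ES with DXA-derived ES:

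1. Replace the ANOVA difference test with the within-person mean difference and its 95% CI, reported in every case, together with limits of agreement.
2. State one margin for EE and one for ES, fixed before the data are seen. Claim agreement in the mean only if the 90% CI lies within the margin.
3. Otherwise report the bias, or state that the result is inconclusive at N=24.
4. State that P>.05 is not evidence of validity.

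Leave the Aim 2 superiority comparison with self-reported intake as a difference test. A margin test is one way to settle agreement in the mean. The essential elements are the interval, the limits of agreement and a criterion fixed beforehand.

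The cost is wording only, with no new data, visits or participants. The small downside is that the team must commit to margins in advance, and ES in particular may have to be reported as inconclusive.
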